Appendix A

	6) Body Mass Index (BMI) ≥ 45 kg/m ² at visit 1 (screening).	Measured 180 days prior to drug initiation any diagnosis position in inpatient or outpatient care setting: Excluding patients with ICD-9 Diagnosis Code (any position) is any of: {"278.01"} 278.01-MORBID OBESITY	
	7) Signed and dated written informed consent by date of visit 1 (screening) in accordance with GCP and local legislation prior to any study related procedure.	N/A	-
	8) High risk of CV events (I and/or II):		
I	Albuminuria (UACR ≥ 30 mg/g creatinine or ≥ 30 µg/min [microgram albumin per minute] or ≥ 30 mg/24 h [milligram albumin per 24 hours] in two out of three unrelated spot urine or timed samples in the last 24 months prior to randomization)* AND previous macrovascular disease, defined as either one or more:		
Ia	Confirmed history of MI (>2 months prior to Visit 1)	Measured from the start of all available data to on the date of drug initiation with diagnosis/procedure position and care setting as noted below:	
Ib	Advanced coronary artery disease, defined by any one of the following: • ≥ 50% narrowing of the luminal diameter in 2 or more major coronary arteries by coronary angiography, MRI angiography or CT angiography; Definition of major coronary arteries: LAD (Left Anterior Descending), CX (Circumflex) or RCA (right coronary artery) • Left main stem coronary artery with ≥ 50% narrowing of the luminal diameter by coronary angiography, MRI angiography or CT angiography; • Prior percutaneous or surgical revascularization of ≥ 2 major coronary arteries at least 2 months prior to Visit 1 (screening); • The combination of prior percutaneous or surgical revascularization of 1 major coronary artery at least 2 months prior to visit 1 (screening), and ≥ 50% narrowing of the luminal diameter by coronary angiography, MRI angiography or CT angiography of at least 1 additional major coronary artery.	Ischemic heart disease in any diagnosis position and inpatient or outpatient care setting: ICD-9 410.xx-414.xx OR Previous cardiac procedure (CABG or PTCA or Stent) in any procedure position and care setting defined below: PTCA: Inpatient CPT-4: 92973, 92982, 92984, 92995, 92996, 92920 – 92921, 92924 – 92925, 92937, 92938, 92941, 92943, 92944 OR – Inpatient or outpatient ICD-9 procedure: 00.66, 36.01, 36.02, 36.03, 36.05, 36.09 Stenting: Inpatient CPT-4: 92980, 92981, 92928 – 92929, 92933 - 92934 OR – Inpatient or outpatient ICD-9 procedure: 36.06, 36.07 CABG: Inpatient CPT-4: 33510 – 33536, 33545, 33572. OR – Inpatient or outpatient ICD-9 procedure: 36.1x, 36.2x Transmyocardial revascularization: Inpatient or Outpatient CPT-4: 33140, 33141 OR -Inpatient or outpatient ICD-9 procedure: 36.31-36.34	Patorno, Elisabetta et al. "Cardiovascular outcomes associated with canagliflozin versus other non-gliflozin antidiabetic drugs: population based cohort study." BMJ 2018;360:k119 http://dx.doi.org/10.1136/bmj.k119 Patorno, Elisabetta et al. "Empagliflozin and the Risk of Heart Failure Hospitalization in Routine Clinical Care: A First Analysis from the Empagliflozin Comparative Effectiveness and Safety (EMPRISE) Study." Circulation . 2019 Apr 8. doi: 10.1161/CIRCULATIONAHA.118.039177
Ic	High-risk single-vessel coronary artery disease, defined as the presence of ≥ 50% narrowing of the luminal diameter of one major coronary artery by coronary angiography, MRI angiography or CT angiography in patients not revascularized: AND at least one of the following: • A positive non invasive stress test, confirmed by either: o a positive ECG exercise tolerance test in patients without left bundle branch block, Wolff-Parkinson-White syndrome, left ventricular hypertrophy with repolarization abnormality, or paced ventricular rhythm, atrial fibrillation in case of abnormal ST-T segments; o a positive stress echocardiogram showing induced regional systolic wall motion abnormalities; o a positive nuclear myocardial perfusion imaging stress test showing stress- induced reversible perfusion abnormality; o a positive cardiac stress perfusion MRI showing a stress induced perfusion defect; • Patient discharged from hospital with a documented diagnosis of unstable angina pectoris between 2 and 12 months prior to visit 1 (screening).		
Id	History of ischemic or haemorrhagic stroke (>3 months prior to visit 1)	Measured from the start of all available data to on the date of drug initiation in any diagnosis position and procedure position in inpatient or outpatient care setting: Any stroke ICD-9 Dx: 430.xx, 431.xx, 433.xx, 434.xx, 436.xx	We including anytime prior to drug initiation here, but then any patients with any stroke within last 3 months are excluded due to the last exclusion criteria.
Ie	Presence of carotid artery disease (symptomatic or not) documented by either: o imaging techniques with at least one lesion estimated to be ≥50% narrowing of the luminal diameter; o prior percutaneous or surgical carotid revascularization.	Measured from the start of all available data to on the date of drug initiation in any diagnosis position and procedure position in inpatient or outpatient care setting: Carotid artery disease ICD-9 433.10 : Occlusion and stenosis of carotid artery without mention of cerebral infarction. ICD-10-CM I65.29 Occlusion and stenosis of unspecified carotid artery	Patorno, Elisabetta et al. "Cardiovascular outcomes associated with canagliflozin versus other non-gliflozin antidiabetic drugs: population based cohort study." BMJ 2018;360:k119 http://dx.doi.org/10.1136/bmj.k119 Patorno, Elisabetta et al. "Empagliflozin and the Risk of Heart Failure Hospitalization in Routine Clinical Care: A First Analysis from the Empagliflozin Comparative Effectiveness and Safety (EMPRISE) Study." Circulation . 2019 Apr 8. doi: 10.1161/CIRCULATIONAHA.118.039177

Appendix A

If
 
Presence of peripheral artery disease documented by either:
 
 o previous limb angioplasty, stenting or bypass surgery; o previous limb or foot amputation due to macrocirculatory insufficiency; o angiographic evidence of peripheral artery stenosis $\geq 50\%$ narrowing of the luminal diameter in at least one limb (definition of peripheral artery: common iliac artery, internal iliac artery, external iliac artery, femoral artery, popliteal artery). 	
Measured from the start of all available data to on the date of drug initiation in any diagnosis position and procedure position in inpatient or outpatient care setting
 
Carotid bypass:
 
ICD9 procedure: 39.28
 
ICD 10 procedure:
 
031H09G Bypass Right Common Carotid Artery to Intracranial Artery with Autologous Venous Tissue, Open Approach
 
031H0AG Bypass Right Common Carotid Artery to Intracranial Artery with Autologous Arterial Tissue, Open Approach
 
031H0J6 Bypass Right Common Carotid Artery to Intracranial Artery with Synthetic Substitute, Open Approach
 
031H0KG Bypass Right Common Carotid Artery to Intracranial Artery with Nonautologous Tissue Substitute, Open Approach
 
031H02G Bypass Right Common Carotid Artery to Intracranial Artery, Open Approach
 
031J09G Bypass Left Common Carotid Artery to Intracranial Artery with Autologous Venous Tissue, Open Approach
 
031J0AG Bypass Left Common Carotid Artery to Intracranial Artery with Autologous Arterial Tissue, Open Approach
 
031J0UG Bypass Left Common Carotid Artery to Intracranial Artery with Synthetic Substitute, Open Approach
 
031J0KG Bypass Left Common Carotid Artery to Intracranial Artery with Nonautologous Tissue Substitute, Open Approach
 
031J0ZG Bypass Left Common Carotid Artery to Intracranial Artery, Open Approach
	

II. Evidence of impaired renal function with predefined UACR, with or without CV co-morbidities, defined as follows (and/or criteria):
 
 - Impaired renal function (as defined by MDRD formula) with an eGFR: 15-<45 mL/min/1.73 m² at visit 1 (screening) with any UACR. - Impaired renal function (as defined by MDRD formula) with an eGFR ≥ 45-75 mL/min/1.73 m² at visit 1 (screening) with an UACR > 200 mg/g creatinine or 
> 200 μg/min (microgram albumin per minute) or > 200 mg/24 h [milligram albumin per 24 hours] demonstrated in two out of three unrelated spot urine or timed samples in the last 24 months prior to randomization.
	
Measured 180 days prior to drug initiation in any diagnosis position in inpatient or outpatient filters:
 
CKD stage 3 and stage 4
 
585.3x-585.4x
	
CKD stage 1: GFR > 90 CKD stage 2: GFR 60 to 89 CKD stage 3a: GFR 45 to 59 CKD stage 3b: GFR 30 to 44 CKD stage 4: GFR 15 to 29 CKD stage 5: GFR < 15

EXCLUSION CRITERIA		

1) Type 1 diabetes mellitus.
	
Measured 180 days prior to drug initiation in any diagnosis position in inpatient or outpatient care setting:
 
DM type 1-At least 1 inpatient or outpatient ICD-9 Dx code of 250.x1 or 250.x3 or ICD-10 Dx code of E10.x in the 12 months prior to drug initiation. 6-months prior
	

2) Treatment (≥ 7 consecutive days) with GLP-1 receptor agonists, other DPP-4 inhibitors or SGLT-2 inhibitors prior to informed consent. Note: This also includes clinical trials where these antidiabetic drugs have been provided to the patient.
	
Measured 180 days prior to drug initiation as a dispensing for one of the following:
 
Treatment (≥ 7 days) with GLP-1 receptor agonists (lixisenatide, dulaglutide, albiglutide, tiraglutide, exenatide), other DPP-4 inhibitors (alogliptin, sitagliptin, saxagliptin) or SGLT-2 inhibitors (canagliflozin, dapagliflozin, empagliflozin) prior to CED
	

3) Active liver disease or impaired hepatic function, defined by serum levels of either ALT (SGPT), AST (SGOT), or alkaline phosphatase (AP) ≥ 3 x upper limit of normal (ULN) as determined at Visit 1.
	
Measured 180 days prior to drug initiation in any diagnosis/procedure position in inpatient or outpatient care setting:
 
Liver disease-ICD-9 diagnosis:
 
070.xx, 570.xx-573.xx 456.0x-456.2x, 576.8x, 782.4x, 789.5x
 
ICD-9 procedure codes:
 
39.1x, 42.91
	
Patorno, Elisabetta et al. "Cardiovascular outcomes associated with canagliflozin versus other non-gliflozin antidiabetic drugs: population based cohort study." BMJ 2018;360:k119 http://dx.doi.org/10.1136/bmj.k119
 
Patorno, Elisabetta et al. "Empagliflozin and the Risk of Heart Failure Hospitalization in Routine Clinical Care: A First Analysis from the Empagliflozin Comparative Effectiveness and Safety (EMPRISE) Study." Circulation. 2019 Apr 8. doi: 10.1161/CIRCULATIONAHA.118.039177

4) eGFR < 15 mL/min/1.73 m² (severe renal impairment or ESRD, MDRD formula), as determined during screening at Visit 1 and/or the need for maintenance dialysis.
	
Measured 180 days prior to drug initiation :
 
CKD stage 5 in any diagnosis/procedure position in inpatient or outpatient care setting- 585.5x OR
 
Dialysis in any diagnosis/procedure position and inpatient care setting:
 
Codes are in the sheet 'Dialysis' Sheet
	

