1.4 Required power for primary endpoint and noninferiority margin (if applicable)

Power- 0.90. Assuming a HR of 1.0, to demonstrate non-inferiority of linagliptin versus placebo within the pre-specified non-inferiority margin of 1.3 at a one-sided α -level of 2.5%.

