6.3.1 Outcome variables

Effectiveness outcomes of interest (definitions provided in **Appendix A**):

- **Primary outcome:** 3-point major adverse cardiovascular events (MACE), i.e., non-fatal myocardial infarction, non-fatal stroke, or CV mortality
- Secondary outcomes: Individual MACE components:
 - Hospital admission for MI (for purposes of this individual component, fatal MI is included)
 - Hospital admission for stroke (for purposes of this individual component, fatal stroke is included)
 - All-cause mortality/CV mortality:
 - All-cause inpatient mortality identified using discharge status codes will be used as a proxy for “CV mortality” in commercial databases
 - Information on CV mortality through data linkage with the National Death Index (NDI) will only become available at a later date for Medicare and will be used in secondary analyses.

Control outcomes of interest (control outcomes only serve to assess aspects of study validity but are not further interpreted):

1. End Stage Renal Disease (we expect to see no association; Rosenstock et al., 2019)

Control outcome definitions

Outcome	Definition	Comments
Control Outcomes		
End Stage Renal Disease (ESRD)	
ESRD with dialysis, defined as:
 
An ICD9 diagnosis (inpatient or outpatient) for ESRD:
 
 ○ 585.5x, Chronic kidney disease, Stage V (for ESRD with no mention of dialysis) ○ 585.6x, End stage renal disease (for ESRD with dialysis) 
AND an ICD9 procedural codes for dialysis (=index date):
 
 ○ 39.95, Hemodialysis ○ 54.98, Peritoneal dialysis 
AND an additional procedural code for dialysis or physician provider code indicating dialysis procedure or ESRD-related activity within two time windows 31-60 and 61-90 days from index date. For patients who die prior to 61 days (31 days), the second (second and first) confirmation requirement(s) can be dropped. This ensures the inclusion of patients with true ESRD outcomes who die early (high early mortality) as well as early withdrawals from dialysis (which lead to high fatality within days or weeks).
	
Note- The corresponding ICD-10 codes will be used also

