After review of initial feasibility and power analyses, complete creation of the remaining covariates (see Table 1 below for list of covariates). Again, using the dummy outcome of a 90-day gap in database enrollment, complete a 1:1 PS-matched analysis. The PS should include the complete list of covariates (excluding laboratory values, which are missing in some patients).

- Provide plot of PS distributions stratified by treatment group.

Note- Please refer to **Appendix B**.

- Report covariate balance after matching.

Note- For Table 1, please refer to **Appendix B**.

- Report reasons for censoring by treatment group.

	Overall	Referent	Exposure
Dummy Outcome	0 (0.00%)	0 (0.00%)	0 (0.00%)
Death	1,704 (1.67%)	929 (1.82%)	775 (1.52%)
Start of an additional exposure	4,752 (4.67%)	746 (1.47%)	4,006 (7.87%)
End of index exposure	58,792 (57.74%)	29,602 (58.14%)	29,190 (57.33%)
Specified date reached	18,168 (17.84%)	9,825 (19.30%)	8,343 (16.39%)
End of patient enrollment	9,190 (9.02%)	4,583 (9.00%)	4,607 (9.05%)
Switch to other SUs (for censoring) + nursing home admission	9,224 (9.06%)	5,230 (10.27%)	3,994 (7.84%)

- Report follow-up time by treatment group.

Patient Group	Median Follow-Up Time (Days) [IQR]		
	Optum	MarketScan	Medicare
Overall Patient Population	118 [58-286]	128 [63-304]	137 [65-323]
Referent	122 [65-304]	148 [86-344]	148 [86-344]
Exposure	118 [58-269]	127 [58-303]	127 [58-303]

- Report overall risk of the primary outcome.

	Optum	Marketscan	Medicare
Risk per 1,000 patients	16.55	18.7	42.47

10. Final Power Assessment

Date conducted: 12/01/2019

- Re-calculate power in the appropriate excel table, using the revised number of matched patients from the PS-match in Section 9. All other parameters in the table should be the same as in Section 8. If the study is to be implemented in more than one database, copy and paste excel sheet to report power for each database separately and for the pooled analysis that uses data from all databases together. Power calculations are based on the formulas from Chow et al. (2008).

- Pooled

Non-inferiority Analysis	
Number of patients matched	
Reference	50,915
Exposed	50,915
Risk per 1,000 patients	25.91
Assumed HR from RCT	1
Alpha (2-sided)	0.05
Non-inferiority margin	1.3
Number of events expected	2638.4153
Power	0.999999116

- Optum

Non-inferiority Analysis	
Number of patients matched	
Reference	8,880
Exposed	8,880
Risk per 1,000 patients	16.55
Assumed HR from RCT	1
Alpha (2-sided)	0.05

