Hypertension: 1 inpatient or 2 outpatient claims within 365 days; n (%)	7,873 (88.7%)	7,855 (88.5%)	6,785 (77.8%)	6,815 (78.2%)	31,536 (94.6%)	31,451 (94.4%)	46,194 (90.7%)	46,121 (90.6%)	.00
Hyperlipidemia ; n (%)	6,695 (75.4%)	6,689 (75.3%)	5,614 (64.4%)	5,628 (64.6%)	26,315 (79.0%)	26,388 (79.2%)	38,624 (75.9%)	38,705 (76.0%)	.00
Edema; n (%)	818 (9.2%)	809 (9.1%)	556 (6.4%)	553 (6.3%)	4,504 (13.5%)	4,434 (13.3%)	5,878 (11.5%)	5,796 (11.4%)	.00
Renal Dysfunction (non-diabetic); n (%)	3,697 (41.6%)	3,732 (42.0%)	2,456 (28.2%)	2,511 (28.8%)	13,956 (41.9%)	14,275 (42.8%)	20,109 (39.5%)	20,518 (40.3%)	.02
Occurrence of acute renal disease; n (%)	643 (7.2%)	603 (6.8%)	422 (4.8%)	419 (4.8%)	2,452 (7.4%)	2,378 (7.1%)	3,517 (6.9%)	3,400 (6.7%)	.01
Occurrence of chronic renal insufficiency; n (%)	3,381 (38.1%)	3,371 (38.0%)	2,101 (24.1%)	2,150 (24.7%)	12,524 (37.6%)	12,774 (38.3%)	18,006 (35.4%)	18,295 (35.9%)	.01
Chronic kidney disease ; n (%)	3,319 (37.4%)	3,314 (37.3%)	2,065 (23.7%)	2,102 (24.1%)	12,176 (36.5%)	12,358 (37.1%)	17,560 (34.5%)	17,774 (34.9%)	.01
CKD Stage 3-4; n (%)	2,764 (31.1%)	2,781 (31.3%)	1,669 (19.1%)	1,702 (19.5%)	9,803 (29.4%)	9,776 (29.3%)	14,236 (28.0%)	14,259 (28.0%)	.00
Occurrence of hypertensive nephropathy; n (%)	1,472 (16.6%)	1,471 (16.6%)	723 (8.3%)	751 (8.6%)	5,364 (16.1%)	5,361 (16.1%)	7,559 (14.8%)	7,583 (14.9%)	.00
Occurrence of miscellaneous renal insufficiency ; n (%)	800 (9.0%)	790 (8.9%)	601 (6.9%)	586 (6.7%)	3,837 (11.5%)	3,718 (11.2%)	5,238 (10.3%)	5,094 (10.0%)	.01
Glaucoma or cataracts ; n (%)	1,689 (19.0%)	1,764 (19.9%)	1,481 (17.0%)	1,507 (17.3%)	9,097 (27.3%)	9,110 (27.3%)	12,267 (24.1%)	12,381 (24.3%)	.00
Cellulitis or abscess of toe; n (%)	166 (1.9%)	138 (1.6%)	82 (0.9%)	101 (1.2%)	570 (1.7%)	591 (1.8%)	818 (1.6%)	830 (1.6%)	.00
Foot ulcer; n (%)	250 (2.8%)	257 (2.9%)	185 (2.1%)	194 (2.2%)	1,091 (3.3%)	1,069 (3.2%)	1,526 (3.0%)	1,520 (3.0%)	.00
Bladder stones; n (%)	17 (0.2%)	16 (0.2%)	17 (0.2%)	17 (0.2%)	70 (0.2%)	66 (0.2%)	104 (0.2%)	99 (0.2%)	.00
Kidney stones; n (%)	290 (3.3%)	272 (3.1%)	270 (3.1%)	260 (3.0%)	1,031 (3.1%)	1,010 (3.0%)	1,591 (3.1%)	1,542 (3.0%)	.01
Urinary tract infections (UTIs); n (%)	1,036 (11.7%)	1,013 (11.4%)	622 (7.1%)	641 (7.4%)	6,198 (18.6%)	6,107 (18.3%)	7,856 (15.4%)	7,761 (15.2%)	.01
Dipstick urinalysis; n (%)	3,574 (40.2%)	3,671 (41.3%)	2,997 (34.4%)	3,094 (35.5%)	15,526 (46.6%)	16,153 (48.5%)	22,097 (43.4%)	22,918 (45.0%)	.03

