...median [IQR]	19.00 [15.00, 25.50]	19.50 [15.00, 27.00]	18.00 [13.50, 24.00]	18.50 [14.00, 26.00]	N/A	N/A	#VALUE!	#VALUE!	#VALUE!
...Missing; n (%)	5,157 (58.1%)	5,041 (56.8%)	8,182 (93.9%)	8,257 (94.7%)	N/A	N/A	13,339 (75.8%)	13,298 (75.6%)	0.00
Lab result number- Creatinine (mg/dl) mean (only 0.1 to 15 included)	3,791	3,936	520	468	N/A	N/A	4,311	4,404	
...mean (sd)	1.20 (0.50)	1.24 (0.51)	1.15 (0.52)	1.18 (0.61)	N/A	N/A	1.19 (0.50)	1.23 (0.52)	-0.08
...median [IQR]	1.08 [0.87, 1.41]	1.14 [0.88, 1.48]	1.00 [0.84, 1.36]	1.01 [0.84, 1.35]	N/A	N/A	1.07 (0.50)	1.13 (0.52)	-0.12
...Missing; n (%)	5,089 (57.3%)	4,944 (55.7%)	8,196 (94.0%)	8,248 (94.6%)	N/A	N/A	13,285 (75.5%)	13,192 (75.0%)	0.01
Lab result number- HDL level (mg/dl) mean (only <5000 included)	2,999	3,087	501	396	N/A	N/A	3,500	3,483	
...mean (sd)	45.64 (13.89)	46.51 (14.12)	43.93 (15.31)	51.64 (174.45)	N/A	N/A	45.40 (14.10)	47.09 (60.26)	-0.04
...median [IQR]	44.00 [36.00, 53.00]	44.50 [37.00, 54.00]	42.50 [35.00, 52.00]	41.00 [34.00, 52.00]	N/A	N/A	43.79 (14.10)	44.10 (60.26)	-0.01
...Missing; n (%)	5,881 (66.2%)	5,793 (65.2%)	8,215 (94.3%)	8,320 (95.5%)	N/A	N/A	14,096 (80.1%)	14,113 (80.2%)	0.00
Lab result number- LDL level (mg/dl) mean (only <5000 included)	3,014	3,106	481	376	N/A	N/A	3,495	3,482	
...mean (sd)	85.21 (41.48)	85.59 (40.41)	86.93 (43.78)	85.05 (45.50)	N/A	N/A	85.45 (41.81)	85.53 (40.99)	0.00
...median [IQR]	81.75 [60.00, 108.00]	82.75 [61.00, 109.00]	85.00 [62.00, 109.58]	84.50 [59.00, 111.38]	N/A	N/A	82.20 (41.81)	82.94 (40.99)	-0.02
...Missing; n (%)	5,866 (66.1%)	5,774 (65.0%)	8,235 (94.5%)	8,340 (95.7%)	N/A	N/A	14,101 (80.1%)	14,114 (80.2%)	0.00
Lab result number- Total cholesterol (mg/dl) mean (only <5000 included)	3,048	3,148	504	402	N/A	N/A	3,552	3,550	
...mean (sd)	172.69 (47.81)	173.80 (47.86)	173.39 (53.59)	173.95 (57.11)	N/A	N/A	172.79 (48.68)	173.82 (49.00)	-0.02
...median [IQR]	166.00 [141.00, 199.00]	166.00 [142.00, 197.50]	168.00 [143.00, 202.88]	170.00 [141.00, 205.00]	N/A	N/A	166.28 (48.68)	166.45 (49.00)	0.00
...Missing; n (%)	5,832 (65.7%)	5,732 (64.5%)	8,212 (94.2%)	8,314 (95.4%)	N/A	N/A	14,044 (79.8%)	14,046 (79.8%)	0.00
Lab result number- Triglyceride level (mg/dl) mean (only <5000 included)	3,015	3,135	499	397	N/A	N/A	3,514	3,532	
...mean (sd)	193.31 (156.70)	189.61 (172.97)	195.78 (174.50)	212.71 (232.81)	N/A	N/A	193.66 (159.37)	192.21 (180.70)	0.01

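### The propensity score has no graded measure of renal function: CKD stages 3 and 4 are one yes/no covariate and labs are excluded, so matching can leave residual renal-severity confounding, as creatinine and BUN suggest where they are measured

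*Combined protocol and SAP*

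**What the plan says.** Appendix A, inclusion criterion 8 (II), uses diagnosis codes for "CKD stage 3 and stage 4" (585.3x-585.4x) as the claims proxy for impaired renal function. The reference column beside it lists "CKD stage 3a: GFR 45 to 59 CKD stage 3b: GFR 30 to 44 CKD stage 4: GFR 15 to 29", so the combined group spans GFR 15 to 59. That is an entry rule, not the PS specification.

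The PS specification comes from Section 6.2, which points to Table 1 for the covariates, and from Section 9: "The PS should include the complete list of covariates (excluding laboratory values, which are missing in some patients". Table 1 (Appendix B) has one row for stages 3 and 4 together and no row for either stage alone. Its other renal rows are:

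- yes/no diagnoses, among them "Occurrence of chronic renal insufficiency; n" and "Renal Dysfunction (non-diabetic); n", plus any CKD, acute renal disease, diabetic nephropathy, hypertensive nephropathy and miscellaneous renal insufficiency;
- counts of creatinine, BUN and microalbuminuria tests ordered.

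The row "Lab result number- Creatinine (mg/dl) mean (only 0.1 to 15 included" is reported for balance only. It is filled for Optum and MarketScan and is N/A for Medicare.

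Section 6.3.1 names one control outcome: "End Stage Renal Disease (we expect to see no association". Section 1.4 sets the test "within the pre-specified non-inferiority margin of 1.3".

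**The concern.** Renal disease is among the larger differences between the arms before matching: the combined stage 3-4 flag is present in 28.1% of linagliptin and 17.3% of sulfonylurea (SU) initiators, standardized difference 0.26. Matching on a flag that covers a fourfold range of GFR equalizes how many patients have the diagnosis, but not necessarily how advanced it is. If severity within or around the flags still differs, the arm with worse renal function carries more risk for reasons unrelated to the drug.

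Two results would be exposed. The ESRD control could depart from its expected null through baseline renal severity alone, which would muddy the only validity check of this kind in the plan. The MACE hazard ratio (HR) could also drift from the trial estimate of 1.02 that it is meant to reproduce.

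**Working it through.** **1. Reproduce the plan's balance figures (Table 1, pooled columns).** For means, standardized difference = (m1 − m2)/√((s1² + s2²)/2).

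- Creatinine, unmatched, SU 1.13 (0.45) vs linagliptin 1.23 (0.53): −0.10/√((0.2025 + 0.2809)/2) = −0.203. Stated −0.20.
- Creatinine, matched, 1.19 (0.50) vs 1.23 (0.52): −0.04/√((0.2500 + 0.2704)/2) = −0.078. Stated −0.08.
- Stage 3-4 flag, matched, 14,236/50,915 = 28.0% vs 14,259/50,915 = 28.0%: −0.001. Stated .00.

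On one scale, the flag went from 0.26 to 0.00 and creatinine from 0.20 to 0.08. In mg/dl the creatinine gap went from 0.10 to 0.04, so matching removed about 60% of it.

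**2. Other renal diagnosis rows, matched, pooled.** Recomputed standardized differences: any CKD −0.009, chronic renal insufficiency −0.012, non-diabetic renal dysfunction −0.016, acute renal disease +0.009, hypertensive nephropathy −0.001, miscellaneous +0.009, diabetic nephropathy −0.005. All lie within about 0.02.

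**3. Is the residual lab gap more than noise?** Unpaired normal approximation, SE = √(s1²/n1 + s2²/n2).

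| Matched comparison | SU | Linagliptin | Gap (95% CI) |
|---|---|---|---|
| Optum creatinine | 1.20 (0.50), n 3,791 | 1.24 (0.51), n 3,936 | 0.04 (0.017 to 0.063), z = 3.48 |
| MarketScan creatinine | 1.15 (0.52), n 520 | 1.18 (0.61), n 468 | 0.03 (−0.04 to 0.10) |
| Pooled creatinine | n 4,311 | n 4,404 | 0.040 (0.018 to 0.061) |
| Optum BUN | 21.39 (9.92), n 3,723 | 22.02 (10.30), n 3,839 | 0.63 (0.17 to 1.09) |

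The Optum BUN standardized difference fell from 0.15 before matching to 0.06 after.

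**4. Coverage.** Creatinine is known for 4,311 + 4,404 = 8,715 of 101,830 matched patients, 8.6%. That is 8,715/35,192 = 24.8% of the commercial patients and none of Medicare, which supplies 66,638/101,830 = 65%.

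**5. Possible size of the bias.** The documents give no risk gradient, so these are assumptions: an HR per 1 mg/dl creatinine of 1.2-2.0 for MACE and 3-10 for ESRD, log-linear, with the lab-subset gap holding in the whole cohort. Spurious HR = (HR per mg/dl)^gap.

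| Gap (mg/dl) | MACE | ESRD |
|---|---|---|
| 0.04 (point estimate) | 1.2^0.04 = 1.007 to 2.0^0.04 = 1.028 | 3^0.04 = 1.045 to 10^0.04 = 1.096 |
| 0.06 (near upper limit) | 1.011 to 1.042 | 1.068 to 1.148 |
| 0.018 (lower limit) | 1.003 to 1.013 | 1.020 to 1.042 |

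**6. Effect on the non-inferiority test.** Power = Φ(√D/2 × ln(1.3/b) − 1.96), with D the expected events in Section 10 and b the spurious HR. At b = 1 this returns the plan's figures: Optum (D = 293.928) 0.614, MarketScan (D = 325.978) 0.659, pooled and Medicare above 0.999. At b = 1.028, Optum falls to 0.521 and MarketScan to 0.563; pooled and Medicare stay above 0.999.

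**The case against.** The best defense is that the combined flag does not stand alone. Seven other renal diagnosis rows, three renal test counts and a comorbidity index are in the PS, and the renal diagnosis rows all balance. The leftover creatinine difference of 0.08 is below the common 0.1 rule of thumb, comes from a small and selected subset, and in MarketScan is compatible with zero. It is displayed in Table 1 for the balance review. Any bias would raise the HR, so it would make non-inferiority harder to show and could not create it falsely. A control outcome that picks up residual renal confounding is doing its job.

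Most of this stands, and it limits the size of the point. It does not remove it. None of the other renal covariates grades severity, so balanced flags alongside unequal creatinine and BUN are what unmatched severity would look like. Medicare has no labs at all, so its balance on severity cannot be inspected from Table 1.

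Three stronger readings are tempting and are not supported:

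- **That the gap reflects extra stage 4 patients hidden in the combined flag.** No stage 3 or stage 4 counts are given. In matched Optum patients the creatinine quartiles are 0.88, 1.14 and 1.48 on linagliptin vs 0.87, 1.08 and 1.41 on SU. The medians differ more than the means, which does not point specifically to stage 4. Moving patients from stage 3 to stage 4 should also widen the SD. If that raises the mean by δ, the variance rises by δ(2(m − 1.20) + g − δ), where m is mean creatinine in stage 3 and g the step to stage 4. Assuming m of 1.3-1.5, g of 0.8-1.5 and δ of 0.02-0.04, the SU SD of 0.50 becomes 0.52-0.58; Table 1 shows 0.51. The shift could equally lie between stages 3a and 3b or among unflagged patients.
- **That the ESRD HR is inflated to 1.1-1.9 and the MACE HR to 1.01-1.09.** Such figures can be produced within the flag, by assuming that at least half the gap sits there and by assuming stage 4 hazards. The flag covers 28% of the pooled cohort, and the planned HR is for the whole cohort.
- **That pooled creatinine imbalance exceeds 0.1.** The −0.12 on the median row divides a difference of averaged medians by SDs. The mean row, −0.08, is the one to cite.

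**Conclusion.** The point holds as a gap in covariate specification with a small visible trace, not as a demonstrated bias. The PS has no graded renal covariate. Where renal function is measured, linagliptin patients are slightly worse after matching on both available markers.

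The 1-4% (MACE) and 4-15% (ESRD) figures run from the point estimate of the gap to about its upper limit. They rest on three assumptions that the documents cannot confirm: the risk gradients, the log-linear form, and the same gap in Medicare and in patients without labs. At the lower limit of the gap they shrink to about 0.3-1.3% and 2-4%. The pooled non-inferiority conclusion is not at risk from an effect of this size. The single-database results and the reading of the ESRD control are more sensitive. This is a worthwhile, inexpensive improvement to control of a large pre-match imbalance.

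**What to change.** In the PS covariate list and Table 1, replace the combined stage 3-4 row with two indicators: stage 3 (585.3x and mapped ICD-10 codes) and stage 4 (585.4x and mapped ICD-10 codes). Keep the combined flag for inclusion criterion 8 (II) only. Re-estimate the PS, re-match in each database, and recheck Optum creatinine and BUN before Section 13 is run; its conduct date is blank in this document.

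If a gap remains, add a creatinine-adjusted sensitivity analysis in the commercial lab subset, comparing adjusted and unadjusted HRs in the same patients. At the database-average risks it would hold about 7,727 × 0.01655 + 988 × 0.0187 = 128 + 18 = 146 MACE events. It can therefore show whether the HR moves with adjustment, but it is too small for a separate non-inferiority test.

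The cost is low. Both codes are already extracted for the inclusion criterion, so no new data are needed. The match is re-run once, and the Section 9 and 10 tables, whose review is already dated December 2019, are refreshed. The split does not separate stages 3a and 3b and does not reach unflagged patients, so it may not close the whole gap.

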5.2 Important steps for cohort formation

5.2.1 Eligible cohort entry dates

Market availability of linagliptin in the U.S. started on May 2, 2011.

- For Marketscan: May 2, 2011-Dec 31, 2017 (end of data availability).
- For Medicare: Jan 1, 2012-Dec 31, 2017 (start- end of data availability).
- For Optum: May 2, 2011-March 31, 2019 (end of data availability).

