Appendix A

Antidiabetic class	Specific agent	Notes
SGLT2-inhibitors	Canagliflozin	Approved 3/29/2013
	Dapagliflozin	
	Empagliflozin	
	Ertugliflozin	Approved Dec 21, 2017
2 nd generation sulfonylureas	Glimepiride	
	Glipizide	
	Glyburide	
DPP-4 inhibitors	Alogliptin	
	Linagliptin	
	Saxagliptin	
	Sitagliptin	
GLP-1 receptor agonist (GLP1-RA)	Exenatide	
	Liraglutide	
	Albiglutide	Approved April 15, 2014 and discontinued July 26, 2017
	Dulaglutide	Approved Sep 18, 2014
	Lixisenatide	Approved July 28, 2016
	Semaglutide	Approved Dec 5, 2017
Insulin	Insulin Aspart	
	Insulin Aspart/Insulin Aspart	
	Protamine	
	Insulin Degludec	
	Insulin Detemir	
	Insulin Glargine	
	Insulin Glulisine	
	Insulin human isophane (NPH)	
	Insulin human regular (search with NPH, don't want bf-pk)	
	Insulin human regular/ Insulin human isophane (NPH)	
	Insulin Lispro	

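### Exclusion 2 is stated by drug class, but its agent list omits semaglutide and ertugliflozin; if that list was run, baseline users of either drug are not excluded, which matters essentially only in Optum

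*Combined protocol and SAP*

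**What the plan says.** In the inclusion/exclusion table of Appendix A, the trial column of Exclusion 2 is written by class: treatment for at least 7 "consecutive days) with GLP-1 receptor agonists, other DPP-4 inhibitors or SGLT-2 inhibitors prior to informed consent". The implementation column turns this into a claims rule, "Measured 180 days prior to drug initiation as a dispensing for one of the following", followed by agents in parentheses. The GLP-1 part reads "GLP-1 receptor agonists (lixisenatide, dulaglutide, albiglutide, tiraglutide, exenatide" (the fourth name looks like liraglutide misread from the PDF). The SGLT-2 part reads "SGLT-2 inhibitors (canagliflozin, dapagliflozin, empagliflozin) prior to CED".

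The antidiabetic class sheet, later in Appendix A, includes semaglutide among the GLP-1 receptor agonists ("Approved Dec 5, 2017") and ertugliflozin among the SGLT-2 inhibitors ("Approved Dec 21, 2017").

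Section 5.2.1 sets the entry windows: "For Optum: May 2, 2011-March 31, 2019 (end of data availability") and "For Marketscan: May 2, 2011-Dec 31, 2017 (end of data availability"). Medicare entry also ends on 31 December 2017. The flowchart row for Exclusion 2 in Section 5.3 is labelled by class and names no agents.

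**The concern.** The criterion and its implementation do not cover the same drugs. As written, the implementation is a closed list: a dispensing of one of the named agents triggers exclusion, and no other agent does. Nothing in the document calls the list illustrative or says that the class sheet overrides it. Where Appendix A wants another sheet used, as for dialysis and pregnancy codes, it says so; Exclusion 2 has no such pointer.

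No other criterion covers the gap. The note on Inclusion 2 sets that criterion aside because Exclusion 2 is meant to do the same work. Applied literally, the rule would therefore let in some patients with baseline use of a class the study intends to exclude. Because the document is to be registered (Section 12), two analysts following its two lists would also build different Optum cohorts.

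**Working it through.** **Step 1: compare the lists.**

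| Class | Class sheet | Exclusion 2 | Missing |
|---|---|---|---|
| GLP-1 receptor agonists | 6 | 5 | semaglutide |
| SGLT-2 inhibitors | 4 | 3 | ertugliflozin |
| DPP-4 inhibitors other than linagliptin | 3 | 3 | none |

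**Step 2: find where the gap can act.** Inputs are the approval dates in the class sheet and the entry windows in Section 5.2.1. Counting both end dates:

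- Optum, approval to 31 March 2019: 482 days for semaglutide, 466 for ertugliflozin.
- MarketScan and Medicare, approval to 31 December 2017: 27 and 11 days, before the 7-day treatment requirement is applied. This is negligible.

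Approval is the earliest possible start; first dispensings in the data may come later.

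**Step 3: size of the window (not of the leak).** Optum entry from 2 May 2011 to 31 March 2019 is 2,891 days, of which 455 fall after 31 December 2017: 455 / 2,891 = 15.7%. Assuming uniform entry, 0.157 × 17,760 matched Optum patients (2 × 8,880) is about 2,800, or 2.7% of the 101,830 patients in the pooled matched cohort. These are entrants in the window; users of the two drugs are an unknown part of them.

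**Step 4: what Table 1 (Appendix B) shows.**

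- Past use of SGLT2i, Optum: 1 referent and 0 linagliptin unmatched; 0 and 0 matched. This limits past ertugliflozin use only if the covariate includes that drug, which is not stated. Continuing users could instead sit in the concomitant/current row.
- There is no row for GLP-1 receptor agonists, so prior semaglutide use can be neither counted nor checked for balance.
- Concomitant initiation or current use of SGLT2i, matched, referent against linagliptin: Optum 51 (0.6%) against 267 (3.0%); MarketScan 62 (0.7%) against 559 (6.4%); Medicare 22 (0.1%) against 412 (1.2%). The row is not split by agent.

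**Step 5: effect on power.** The plan's Optum figure reproduces with power = Φ(√D/2 × ln 1.3 − 1.96):

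- D = 17,760 × 16.55 / 1,000 = 293.928.
- √293.928 / 2 × 0.2624 − 1.96 = 0.289, and Φ(0.289) = 0.614 (Section 10 gives 0.613734405).

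Removing assumed numbers of matched Optum patients:

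| Removed (assumed) | Expected events | Optum power |
|---|---|---|
| 50 | 293.1 | 0.613 |
| 318 (all matched Optum concomitant/current SGLT2i users, 51 + 267) | 288.7 | 0.606 |
| 1,000 | 277.4 | 0.589 |

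Pooled, using the plan's risk of 25.91 per 1,000 and 1,000 patients removed: 100,830 × 25.91 / 1,000 = 2,612.5 events, and power stays above 0.99999.

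**The case against.** The strongest reply is that the mismatch may exist only on paper. The rule is stated by class in the trial wording, in the note on Inclusion 2 and in the flowchart label; the class sheet sits in the same appendix and may be what was coded. Appendix A also sends readers to an external folder for missing details. This stands: entry of such patients follows from the written list but is not observed, so the point must be conditional.

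A reader might also infer that any leak falls mainly in the linagliptin arm, because matched Optum patients show 3.0% against 0.6% on concomitant or current SGLT2i. The documents do not support that. The row mixes drugs started together with drugs already in use. The same direction of imbalance appears in MarketScan and Medicare, where the two omitted drugs could hardly matter, and the MarketScan gap is larger than the Optum one. Something other than the omitted drugs must produce much of the pattern.

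A third temptation is to treat everyone who entered Optum after the approvals as affected. The window figures rest on uniform entry and on approval dates standing in for first use, and they count entrants, not users of either drug.

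Finally, a re-run is not trivial: balance and power were reviewed by the principal investigator and FDA in December 2019 (Section 10). That argues for checking the code first, not for leaving the lists unreconciled.

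**Conclusion.** The point holds as a small, conditional internal inconsistency. The class-level criterion and its agent list disagree on two drugs, and the document does not say which list governs. If the short list was executed, baseline users of semaglutide or ertugliflozin remain eligible, in practice only in Optum and only late in its entry window. The number is not given and is probably small, a judgement that rests partly on the past-use SGLT2i covariate including ertugliflozin. For semaglutide the document offers no evidence either way, and the arm in which a leak would fall is unknown. Power is not at stake in any material sense.

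**What to change.** Reconcile the two parts of Appendix A: have Exclusion 2 refer to the class sheet, so that its agent list matches the classes it states. Then check which list the executed code used.

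- If it used the class sheet, correct the text only.
- If it used the short list, add semaglutide and ertugliflozin, report the number removed from Optum, and re-run the Optum cohort, propensity-score match, balance table and power, with the pooled figures updated. Do this before the comparative analysis in Section 13, whose date is still blank.

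The text change costs almost nothing. The second route costs a modest Optum re-run and a renewed review of Sections 9 and 10.
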